**SYNOPSIS**

Study Title:	A Randomized, Multicenter, Open-label, Phase 3 Study of the Bruton's Tyrosine Kinase Inhibitor Ibrutinib in Combination with Obinutuzumab versus Chlorambucil in Combination with Obinutuzumab in Subjects with Treatment-naive Chronic Lymphocytic Leukemia or Small Lymphocytic Lymphoma
Protocol Number:	PCYC-1130-CA
Study Phase:	3
Study Duration:	Estimated to be 4 years
Investigational Product and Reference Therapy:	Ibrutinib will be supplied as 140 mg hard gelatin capsules for oral (PO) administration. Obinutuzumab will be supplied as 1000 mg/40 mL solution in a single-use vial for intravenous (IV) administration Chlorambucil will be supplied as 2 mg film-coated tablets for oral (PO) administration
Objectives:	
Primary Objective: To evaluate the efficacy of ibrutinib in combination with obinutuzumab compared to chlorambucil in combination with obinutuzumab based on the Independent Review Committee (IRC) assessment of progression-free survival (PFS) in subjects with treatment-naive chronic lymphocytic leukemia (CLL) or small lymphocytic lymphoma (SLL)
 
Secondary Objectives: To compare the treatment groups in terms of the following:
 
Efficacy
 
 
• Overall response rate (ORR) according to International Workshop on Chronic Lymphocytic Leukemia (IWCLL) 2008 criteria, as assessed by the IRC
 
• Rate of minimal residual disease (MRD)-negative responses
 
• Overall Survival
 
• Hematological improvement measured by platelet and hemoglobin counts
 
• Patient-reported outcomes (PRO) as measured by European Organisation for Research and Treatment of Cancer Quality of Life Questionnaire EuroQoL Five-Dimension (EQ-5D-5L)
 
 
Safety
 
 
• To evaluate the safety and tolerability of ibrutinib in combination with obinutuzumab compared with chlorambucil in combination with obinutuzumab
 
• To evaluate obinutuzumab-related infusion reactions by treatment arm
 

	
Exploratory Objectives:
 
To evaluate the treatment groups in terms of the following:
 
 
• Event-free survival
 
• Time to next treatment
 
• Clonal evolution - acquisition of new cytogenetic abnormalities
 
• Potential predictive biomarkers of efficacy and/or mechanisms of resistance
 
• Medical resource utilization (MRU) (eg, requirements of hospitalizations, transfusions and use of growth factors)
 
• Sparse pharmacokinetic (PK) characteristics of ibrutinib in patients with CLL or SLL, and which, if any, covariates (eg, age, sex, body size, or race) influence exposure to ibrutinib
 
• Examination of genetic and molecular prognostic markers
 


Study Design:
	
This is a Phase 3, multicenter, randomized, open-label study of oral ibrutinib in combination with intravenous obinutuzumab versus oral chlorambucil in combination with intravenous obinutuzumab in subjects with treatment-naïve chronic lymphocytic leukemia or small lymphocytic lymphoma.
 
Eligible subjects will be randomized in a 1:1 ratio to Treatment Arm A or Treatment Arm B:
 
Arm A: Ibrutinib + Obinutuzumab
 
Oral ibrutinib 420 mg daily (3 capsules) continuously (until evidence of progressive disease or no longer tolerated by the patient) in combination with obinutuzumab 1000 mg intravenously over 6 cycles: Days 1+2 (100 mg on Day 1 and 900 mg on Day 2), 8 and 15 of Cycle 1 followed by Day 1 only on Cycles 2-6.
 
Arm B: Chlorambucil + Obinutuzumab
 
Treatment will be 6 cycles. Chlorambucil will be administered orally at a dose of 0.5 mg/kg body weight, on Days 1 and 15 of each cycle. Obinutuzumab will be administered intravenously at a dose of 1000 mg, over 6 cycles: given on Days 1+2 (100 mg on Day 1 and 900 mg on Day 2), 8 and 15 of Cycle 1 and on Day 1 only on Cycles 2-6.
 
Treatment will be administered up to a maximum of 6 cycles or until disease progression or unacceptable toxicity, whichever occurs first.
 
Approximately 212 subjects will be randomized. Two randomization schemes will be generated: one for each geographic region (North America versus Rest of World). Under each scheme, randomization will be stratified according to:
 
 
• Eastern Cooperative Oncology Group (ECOG) performance status of 0-1 vs 2
 
• Cytogenetics – will be stratified into one of three categories 
 
○ del 17p
 
○ del 11q without del 17p
 
○ others (neither del 17p nor del 11q)
 
 
 

	
Assessment of disease response and progression will be conducted in accordance with IWCLL 2008 criteria, with the modification that isolated treatment-related lymphocytosis will not be considered as disease progression, as recommended by the National Comprehensive Cancer Network (NCCN) 2012 guidelines and further defined in Section 7.2.3.
 
During the Pre-PD Phase, subjects will undergo regular scheduled assessments. Response evaluations will be continued every 4 cycles from the initial dose with study drug until Cycle 33 response assessment and then every 6 cycles until disease progression.
 
Subjects randomized to Arm B (chlorambucil in combination with obinutuzumab) who experience IRC-confirmed disease progression can be eligible for access to next-line ibrutinib (cross-over) therapy.
 
Subjects in either arm who discontinue treatment in the absence of disease progression will remain on study until IRC-confirmed disease progression or study closure.
 
All subjects will undergo an End-of-Treatment Visit up to 30 days after discontinuation of randomized treatment (and/or discontinuation of ibrutinib cross-over therapy for subjects randomized to Treatment Arm B) or prior to starting a new anticancer treatment.
 
All subjects then will be followed for survival and subsequent anti-cancer therapies.
 
A summary flow diagram of the study design is found in Section 3.1.1.
 
An independent Data Monitoring Committee (DMC) will monitor the safety of the study.

Population:	Treatment-naïve chronic lymphocytic leukemia or small lymphocytic lymphoma with active disease requiring therapy
Centers:	Multiple, International

Inclusion Criteria:
 
Refer to Section 4 for the complete and detailed list of inclusion/exclusion criteria.
	
Disease Related
 
 
1. Diagnosis of CLL/SLL that meets IWCLL diagnostic criteria (Hallek 2008)
 
2. Age 65 yrs and older OR if less than 65 years old, must have at least one of the following criteria: 
 
a) Cumulative Illness Rating Score (CIRS) >6
 
b) Creatinine clearance <70 mL/min using the Cockcroft-Gault equation
 
c) Del 17p by FISH or TP53 mutation by PCR or Next Generation Sequencing (NGS)
 
 
 
3. Active disease meeting at least 1 of the following IWCLL criteria (Hallek 2008) for requiring treatment: 
 
a) Evidence of progressive marrow failure as manifested by the development of, or worsening of, anemia and/or thrombocytopenia
 
b) Massive, progressive, or symptomatic splenomegaly
 
c) Massive nodes or progressive or symptomatic lymphadenopathy
 
d) Progressive lymphocytosis
 
 
 

	
e) Autoimmune hemolytic anemia and/or immune thrombocytopenia that is poorly responsive to corticosteroids or other standard therapy
 
f) Constitutional symptoms
 
4. Measurable nodal disease by computed tomography (CT)
 
Laboratory
 
5. Adequate hematologic function independent of transfusion and growth factor support for at least 7 days prior to Screening and randomization:
 
a) Absolute neutrophil count <math>\geq 1.0 \times 10^9/L</math>
 
b) Platelet count <math>>50 \times 10^9/L</math>
 
6. Adequate hepatic and renal function defined as:
 
 
o Serum aspartate transaminase (AST) or alanine transaminase (ALT) <math>\leq 2.5 \times ULN</math>.
 
o Estimated Creatinine Clearance <math>\geq 30</math> mL/min (Cockcroft-Gault)
 
o Bilirubin <math>\leq 1.5 \times ULN</math> (unless bilirubin rise is due to Gilbert's syndrome or of non-hepatic origin)
 
 
Demographic
 
7. Men and women <math>\geq 18</math> years of age.
 
8. Eastern Cooperative Oncology Group (ECOG) performance status of 0 to 2.
 
Ethics/other
 
9. Willingness to receive all outpatient treatment, all laboratory monitoring, and all radiological evaluations at the institution that administers study drug for the entire study
 
10. Ability to provide written informed consent and to understand and comply with the requirements of the study
 
11. Female subjects who are of non-reproductive potential (ie, post-menopausal by history - no menses for <math>\geq 1</math> year; OR history of hysterectomy; OR history of bilateral tubal ligation; OR history of bilateral oophorectomy). Female subjects of childbearing potential must have a negative serum pregnancy test upon study entry.
 
12. Male and female subjects who agree to use highly effective methods of birth control (eg, condoms, implants, injectables, combined oral contraceptives, some intrauterine devices [IUDs], sexual abstinence, or sterilized partner) during the period of therapy and for 90 days after the last dose of ibrutinib/chlorambucil or obinutuzumab, and at least 18 months after the last obinutuzumab dose for female subjects.

Exclusion Criteria:	
Concurrent Conditions
 
1. Any prior chemotherapy, radiotherapy, small molecule inhibitors including kinase inhibitors, and/or monoclonal antibody used for treatment of CLL or SLL
 
2. Evidence of central nervous system (CNS) involvement with primary disease of CLL/SLL
 
3. History of other malignancies, except:

	

a) Malignancy treated with curative intent and with no known active disease present for <math>\geq 3</math> years before the first dose of study drug and felt to be at low risk for recurrence by treating physician.

b) Adequately treated non-melanoma skin cancer or lentigo maligna without evidence of disease.

c) Adequately treated carcinoma in situ without evidence of disease.

 

4. Uncontrolled autoimmune hemolytic anemia or idiopathic thrombocytopenic purpura

5. Known or suspected history of Richter's transformation

6. Concurrent administration of <math>>20</math> mg/day of prednisone within 7 days of randomization unless indicated for prophylaxis or management of allergic reactions (eg, contrast)

7. Known hypersensitivity to one or more study drugs

8. Vaccinated with live, attenuated vaccines within 4 weeks of first dose of study drug.

9. Any uncontrolled active systemic infection or an infection requiring systemic treatment that was completed <math>\leq 7</math> days before randomization.

10. Known bleeding disorders (eg, von Willebrand's disease or hemophilia).

11. History of stroke or intracranial hemorrhage within 6 months prior to enrollment.

12. Known history of human immunodeficiency virus (HIV) or active with hepatitis B virus (HBV) or hepatitis C virus (HCV). Subjects who are positive for hepatitis B core antibody, hepatitis B surface antigen, or hepatitis C antibody must have a negative polymerase chain reaction (PCR) result before enrollment. Those who are PCR positive will be excluded.

13. Major surgery within 4 weeks of randomization.

14. Any life-threatening illness, medical condition, or organ system dysfunction that, in the investigator's opinion, could compromise the subject's safety or put the study outcomes at undue risk.

15. Currently active, clinically significant cardiovascular disease, such as uncontrolled arrhythmia or Class 3 or 4 congestive heart failure as defined by the New York Heart Association Functional Classification; or a history of myocardial infarction, unstable angina, or acute coronary syndrome within 6 months prior to randomization.

16. Unable to swallow capsules or malabsorption syndrome, disease significantly affecting gastrointestinal function, or resection of the stomach or small bowel, symptomatic inflammatory bowel disease or ulcerative colitis, or partial or complete bowel obstruction.

17. Concomitant use of warfarin or other Vitamin K antagonists.

18. Requires treatment with a strong cytochrome P450 (CYP) 3A inhibitor (see Appendix C).

19. Lactating or pregnant.

20. Unwilling or unable to participate in all required study evaluations and procedures.

--	------------------------------------------------------------------------------------------------------------------------------------------------------------------------------------------------------------------------------------------------------------------------------------------------------------------------------------------------------------------------------------------------------------------------------------------------------------------------------------------------------------------------------------------------------------------------------------------------------------------------------------------------------------------------------------------------------------------------------------------------------------------------------------------------------------------------------------------------------------------------------------------------------------------------------------------------------------------------------------------------------------------------------------------------------------------------------------------------------------------------------------------------------------------------------------------------------------------------------------------------------------------------------------------------------------------------------------------------------------------------------------------------------------------------------------------------------------------------------------------------------------------------------------------------------------------------------------------------------------------------------------------------------------------------------------------------------------------------------------------------------------------------------------------------------------------------------------------------------------------------------------------------------------------------------------------------------------------------------------------------------------------------------------------------------------------------------------------------------------------------------------------------------------------------------------------------------------------------------------------------------------------------------------------------------------------------------------------------------------------------------------------------------------------------------------------------------------------------------------------------------------------------------------------------------------------------------------------------------------------------------------------------------------------------------------------------------------------------------------------------------------------------------------------------------------------------------------------------------------------------------------------------------------------------------------------------------------------------------------------------------

	
21. Unable to understand the purpose and risks of the study and to provide a signed and dated informed consent form (ICF) and authorization to use protected health information (in accordance with national and local subject privacy regulations)

Study Treatment:
	
1:1 Randomization between Arm A & Arm B
 
Arm A: Ibrutinib + Obinutuzumab
 
Oral ibrutinib 420 mg daily (3 capsules) continuously (until evidence of progressive disease or no longer tolerated by the subject) in combination with obinutuzumab 1000 mg intravenously over 6 cycles: Days 1+2 (100 mg on Day 1 and 900 mg on Day 2), 8 and 15 of Cycle 1 followed by Day 1 only on Cycles 2-6.
 
Intravenous obinutuzumab will be administered per Section 5.3.2.3. The first dose of ibrutinib will be taken in the clinic, after which ibrutinib will be issued to the subject as an ongoing 28-day supply for home administration.
 
Arm B: Chlorambucil + Obinutuzumab
 
Treatment will be 6 cycles. Chlorambucil will be administered orally at a dose of 0.5 mg/kg body weight, on Days 1 and 15 of each cycle. Obinutuzumab will be administered intravenously at a dose of 1000 mg over 6 cycles: given on Days 1+2 (100 mg on Day 1 and 900 mg on Day 2), 8 and 15 of Cycle 1 and on Day 1 only on Cycles 2-6.
 
Treatment will be administered up to a maximum of 6 cycles or until disease progression or unacceptable toxicity, whichever occurs first.
 
Intravenous obinutuzumab will be administered per Section 5.3.2.3 Chlorambucil will be administered in the clinic on days which coincide with concomitant obinutuzumab (Days 1 + 15 of Cycle 1 and Day1 of Cycles 2-6) and will be issued to the subject for home administration on other occasions (Day 15 of Cycles 2-6).
 
Next-line ibrutinib monotherapy:
 
Access to next-line ibrutinib monotherapy (cross-over) for subjects treated in Arm B may be provided after confirmed disease progression (by the IRC) and approval of the medical monitor.

Concomitant Therapy:
	
Refer to Section 6 for information on concomitant therapy.
 
Any chemotherapy, anticancer immunotherapy, corticosteroids (at dosages equivalent to prednisone >20 mg/day), experimental therapy, or radiotherapy is prohibited or as otherwise detailed in Section 6.1.


Safety Plan:
 
Refer to Section 10.1.2 and DMC charter for details.
	
The safety of this study will be monitored by an independent Data Monitoring Committee (DMC) as outlined in the DMC Charter and in accordance with the Sponsor’s Pharmacovigilance procedures.
 
A safety review of subjects randomized to the ibrutinib and obinutuzumab arm (Arm A) will be conducted after the first six subjects have completed one cycle of treatment.

**Statistical Methods and Data Analysis:**

Efficacy analyses will be performed using the intent-to-treat (ITT) population.

**Primary Efficacy Analysis:**

The primary endpoint of this study is progression-free survival (PFS) as assessed by IRC review, according to IWCLL 2008 criteria. PFS will be analyzed comparing the 2 treatment arms using a log-rank test. Distribution of PFS will be summarized for each treatment arm using the Kaplan-Meier estimate of median and its corresponding 95% confidence interval (CI). The estimate of the hazard ratio and its corresponding 95% CI will be computed using a Cox proportional hazards model.

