### **1.1.3. Chronic Lymphocytic Leukemia with 17p Deletion and/or TP53 mutation**

Apart from age and co-morbidity, a number of intrinsic genetic and molecular abnormalities have been characterized which also identify subgroups of CLL patients who generally have an adverse clinical course and a poor outcome to therapy. These include del 17p, del 11q, IgVH unmutated status, use of the IGHV3-21 gene segment and expression of either ZAP70 or CD38 (Krober 2002; Krober 2006). However, it is widely acknowledged that chromosomal 17p deletion is the pre-eminent adverse prognostic parameter, with the majority of patients belonging to an “ultra-high-risk” group characterized by the worst possible overall outcome (Stilgenbauer 2010).

Approximately 10% of patients with CLL in the first line treatment setting carry the del 17p abnormality (Dohner 2000). As the TP53 tumor suppressor gene, which plays a critical role in oncogenesis and response to DNA damaging chemotherapy (Hollstein 1991; Pietsch 2008) is located on the short arm of chromosome 17, over eighty per cent of del 17p deletions are also associated with concomitant p53 dysfunction of some sort (Rossi 2009).

The associated loss of p53 integrity may explain why the del 17p abnormality is the poorest prognostic factor for CLL. So integral in fact is the del 17p/TP53 axis to determining chemoresponsiveness in CLL, that it has been postulated as the only biomarker currently available for driving treatment decisions in the management of the disease (Mertens 2014).

The presence of a TP53 mutation can however also occur in the absence of a del 17p chromosomal abnormality, in approximately five percent of cases of CLL (Rossi 2009; Dicker 2009) and is an equally poor prognostic factor, independent of 17p status (Zenz 2008; Oscier 2002).

Both 17p deletion and TP53 mutation are therefore powerful prognostic markers for non-response to currently available CLL therapy. Patients with these abnormalities have exceptionally poor outcomes with chemoimmunotherapy regimens such as FCR, due in large part to lack of p53 function, which is an important pathway for mediating the cytotoxicity of many drugs, including purine analogs, such as fludarabine (Dohner 1995).

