#### **7.1.3.5. Genetic and Molecular Prognostic Markers**

A blood sample will be collected from all subjects during Screening and analyzed centrally to examine pretreatment prognostic factors.

These will include immunoglobulin heavy-chain variable (IgVH) and other genes known to be involved in CLL prognosis (eg, TP53, and Notch 1, SF3B1) mutational status.

In addition, genomic profiling of the tumor cells may be performed at baseline, during treatment or at progression as needed.

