**10.7.3.7. Genetic and Molecular Prognostic Markers**

Genetic and molecular prognostic markers will be summarized with descriptive statistics.

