1.3. Statistical Hypotheses

The primary hypothesis of this study is that the experimental treatment ibrutinib + obinutuzumab compared with chlorambucil + obinutuzumab will significantly improve PFS in subjects diagnosed with CLL or SLL who are treatment-naive but now require active therapy.

The statistical hypotheses are as follows:

H_0 : The PFS distributions of experimental treatment group, $S_I(t)$, and the control group, $S_C(t)$, are equal at all time points t :

$$S_I(t) = S_C(t), \text{ for all } t > 0$$

versus

H_1 : The PFS distributions of experimental treatment group, $S_I(t)$, are different from the control group, $S_C(t)$, at at least one time point t :

$$S_I(t) \neq S_C(t), \text{ for some } t > 0$$

These hypotheses will be tested using a 2-sided stratified log-rank test at α level of 0.05.

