4. ANALYSIS FOR ENDPOINTS

Analysis of endpoints will be conducted on the ITT population, unless otherwise specified. Table 1 summarizes the efficacy endpoints and analysis methods to be performed.

The following two randomization stratification factors will be used for the stratified analysis/test: ECOG performance status (0, 1 versus 2) and Cytogenetics (del 17p, del 11q without del 17p, others). To reflect the randomization process and maintain the integrity of randomization, all stratified tests will be based on randomization stratification factors as recorded in the IWRS.

For subgroup and exploratory analysis, only the analysis that provide meaningful information will be presented.

Table 1: Definitions and Analyses for Endpoints

Endpoint	Definition	Analysis Method
Primary Endpoint		
PFS assessed by IRC	Time from the date of randomization to the date of IRC-assessed disease progression or date of death from any cause, whichever occurred first, regardless of the use of subsequent antineoplastic therapy prior to documented PD or death.	
Primary Treatment effect of ibrutinib plus obinutuzumab compared to chlorambucil plus obinutuzumab was tested with a log-rank test. The hazard ratio and its 95% CI based on a Cox regression model are calculated. PFS distribution is estimated by Kaplan-Meier method: median PFS and landmark estimates with 2-sided 95% CIs are to be provided for each treatment arm.
 
Sensitivity Analyzing PFS assessed by investigator using the same method as PFS assessed by IRC.
 
Subgroup Hazard ratio and its 95% CI based on unstratified Cox regression model for each subgroup.

Secondary Endpoints		
PFS assessed by IRC in high risk analysis set	Defined the same as the primary endpoint.	Analyzed the same as primary endpoint in high risk analysis set
ORR assessed by IRC	The proportion of subjects achieving a best overall response of CR, CRi, nPR, or PR per IRC assessment at or prior to initiation of subsequent antineoplastic therapy.	Chi-square test.
Overall survival (OS)	Time from the date of randomization to the date of death from any cause. All deaths observed at the time of the analysis will be considered as events. For subjects who were not known to have died at the time of the analysis, OS data will be censored at date last known alive.	Analyzed the same as PFS primary analysis.

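### IGHV status is named as an adverse prognostic factor and measured at Screening in every subject, but no PFS analysis uses it as a covariate: a missed efficiency gain, not an error

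*Protocol*

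**What the plan says.** **The primary analysis.** The protocol (synopsis and 10.7.1) compares IRC-assessed PFS by a log-rank test and adds a Cox model: "The estimate of the hazard ratio and its corresponding 95% CI will be computed using a Cox proportional hazards model". SAP 1.3 makes the test stratified: "These hypotheses will be tested using a 2-sided stratified log-rank test at α level of 0.05". SAP section 4 names the factors: "The following two randomization stratification factors will be used for the stratified analysis/test: ECOG performance status (0, 1 versus 2) and Cytogenetics", taken as recorded in the IWRS. SAP Table 1 says only "The hazard ratio and its 95% CI based on a Cox regression model are calculated" and omits the word stratified for both test and model, although its subgroup entry specifies an unstratified model. Read together, the primary test is stratified by ECOG and cytogenetics, and the Cox model is presumably meant to be.

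**IGHV.** Protocol 1.1.3, on abnormalities that mark a poor course, says: "These include del 17p, del 11q, IgVH unmutated status". Protocol 7.1.3.5 takes a Screening blood sample from all subjects for central analysis of prognostic factors: "These will include immunoglobulin heavy-chain variable (IgVH) and other genes known to be involved in CLL prognosis". The planned use, in 10.7.3.7, is: "Genetic and molecular prognostic markers will be summarized with descriptive statistics". IGHV is not a randomization factor and is not part of the SAP's high risk analysis set. The SAP lists the abbreviation, but its available text gives IGHV no analysis. SAP 2.2 does not name the subgroup variables, so use as a subgroup cannot be excluded.

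**The concern.** A prognostic baseline covariate that is already collected can sharpen a time-to-event comparison at little cost, provided its use is fixed in advance. Two features of this trial make that worth considering.

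- There is little spare power. The plan aims at about 80% with 94 events and no interim analysis, and SAP 1.6 places all eight secondary endpoints behind PFS in a serial gatekeeping procedure.
- Randomization does not balance IGHV directly. With 106 subjects per arm and an assumed 60% unmutated, the arms can differ by chance by about 1.96 × √(2 × 0.6 × 0.4 / 106) = 0.13, or 13 percentage points. An adjustment chosen after the results are known would carry little weight; one written down beforehand would.

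**Working it through.** **1. The plan's own figure.** Inputs from Protocol 10.3 and SAP 1.4: hazard ratio 0.55, 1:1 allocation, two-sided 5%, 80% power, medians 27 and 49.1 months, 212 subjects, 18 per month.

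- Median: 27 / 0.55 = 49.1 months, as stated.
- Freedman: (1.96 + 0.842)² × (1.55 / 0.45)² = 7.85 × 11.86 = 93.1, rounded up to 94 events, as stated. Power at 94 events is Φ(√94 × 0.45 / 1.55 − 1.96) = Φ(0.855) = 80.4%.
- Schoenfeld: 4 × 7.85 / (ln 0.55)² = 87.8, or 88 events. Power at 94 events is 82.6%.
- Expected events at 36 months under uniform accrual and exponential PFS: 93.5.

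The plan reproduces without any reference to IGHV.

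**2. What adjustment changes.** The documents give no IGHV frequency or prognostic effect, so both are assumed. Each simulation has 212 subjects, cutoff at the 94th event, six strata (two ECOG × three cytogenetic) and a treatment hazard ratio of 0.55 within each IGHV level. It compares the stratified log-rank test without IGHV against a Cox model with the same strata plus IGHV as a covariate. Power, without → with IGHV:

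| Prognostic HR of unmutated IGHV | 50% unmutated (3,000 trials) | 60% unmutated (4,000 trials) | 60% unmutated (separate run) |
|---|---|---|---|
| 1.0 | not run | 81.8% → 81.4% | 79.2% → 78.7% |
| 1.5 | 80.4% → 80.0% | 79.8% → 80.8% | 80.1% → 79.8% |
| 2 | 78.3% → 80.5% | 78.7% → 80.7% | 75.1% → 77.8% |
| 3 | 73.9% → 79.4% | 76.8% → 80.7% | 74.7% → 79.6% |

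The 4,000-trial column assumes 10% ECOG 2, 10% del 17p and 15% del 11q, with prognostic hazard ratios of 1.5, 2.5 and 1.5. The Monte Carlo standard error of a single power figure is about √(0.8 × 0.2 / 4,000) = 0.6 points (0.7 with 3,000 trials), so small differences in level between columns mean little. The change within a cell is what matters: −0.5 to −0.4 points at 1.0, −0.4 to +1.0 at 1.5, +2.0 to +2.7 at 2, and +3.9 to +5.5 at 3. Extending the first column's setting to 65% unmutated stays within a gain of about 0 to 5.5 points. One-sided type I error of the adjusted test was 2.3-2.6%.

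**3. The hazard ratio.** In the 4,000-trial setting the average estimate without IGHV is 0.550, 0.556 and 0.568 at prognostic hazard ratios of 1.5, 2 and 3. With IGHV it is about 0.546 throughout. The gap arises because a hazard ratio averaged over a prognostic factor differs from one conditional on that factor, even when the factor is balanced between arms.

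**4. If 0.55 is the overall hazard ratio.** Setting the within-level hazard ratio to 0.535 or 0.52, so that the analysis with neither strata nor IGHV returns about 0.55, gives stratified power of 82.8% → 84.1% at prognostic hazard ratio 2 and 83.7% → 87.6% at 3.

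**5. If IGHV matters only in the control arm** (60% unmutated, prognostic hazard ratio 2, no other strata), the hazard ratio without IGHV stays at 0.549, and power moves from 82.4% to 84.2% with adjustment.

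**The case against.** The strongest reply is that nothing in the plan needs repair. Stratifying by the randomization factors is a valid choice that SAP section 4 justifies, and del 17p, which Protocol 1.1.3 ranks as the leading adverse factor, is already among them. That stands.

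Two stronger readings are tempting, and the documents support neither.

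- **That leaving out IGHV makes the trial underpowered.** The target of 0.55 comes from overall arm medians of 27 and 49.1 months, so it is most naturally an overall hazard ratio. On that reading the plan keeps its 80%, and adjustment adds power above it (step 4). A shortfall appears only if 0.55 is taken to hold within IGHV levels.
- **That the planned hazard ratio is biased or understates the effect.** The hazard ratios with and without IGHV are different estimands, and neither is a biased version of the other. Protocol 1.1.4 also suggests that ibrutinib works regardless of adverse factors; if so, the treatment effect may differ by IGHV status and there is no single conditional value to recover (step 5).

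It is also fair to say that the gain is uncertain, and that replacing the log-rank as confirmatory test would change both documents in an open-label trial. Reporting an adjusted model only as supportive leaves confirmatory power as it is. None of this argues against pre-specifying the adjusted estimate.

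**Conclusion.** The point holds as an optional improvement. The planned PFS analysis is valid and its event count reproduces; it simply makes no pre-specified use of a named prognostic factor that every subject has measured centrally before treatment.

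Assuming 50-65% unmutated and the same treatment effect within each IGHV level, adding IGHV as a covariate is worth about 0-1 power point at a prognostic hazard ratio of 1.5, 2-3 points at 2 and 4-5.5 points at 3. If IGHV is not prognostic, nothing is gained and the simulated loss is about half a point. These figures depend on frequencies and effects that the documents do not give; the upper end needs a strong IGHV effect.

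**What to change.** Before database lock, add to SAP section 4 and Table 1 a Cox model for IRC-assessed PFS, stratified by the IWRS ECOG and cytogenetic factors, with baseline IGHV status (mutated / unmutated / unknown, from the Screening sample) as a covariate. Report its hazard ratio, 95% CI and two-sided test, and label the hazard ratio as conditional on IGHV. In the same edit, state in Table 1 that the primary log-rank test and Cox model are stratified.

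Keep the stratified log-rank as the confirmatory test and name the adjusted model as the key supportive analysis, outside the gatekeeping sequence. The alternative is for the sponsor to decide, before unblinding, to make the adjusted model primary. That requires changing the protocol (synopsis and 10.7.1) as well as SAP 1.3 and section 4, and only then does the power gain reach the confirmatory test.

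Do not add IGHV as a further stratification factor: even a two-level factor would turn six already sparse strata into twelve.

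The cost is a few lines of SAP text, one extra model term, an unknown level for missing results and a second hazard ratio that readers must be told is conditional. No new samples, visits or subjects are needed.
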